9 STATISTICAL CONSIDERATIONS

9.1 Statistical Hypotheses

The hypotheses for the primary efficacy endpoint for each indication and dose level are given as follows:

Monotherapy Dose Expansion:

H0: iORR is 10%, at which the treatment is deemed as unacceptable.

H1: iORR is at least 25%, at which the treatment is deemed as acceptable.

Combination Therapy Dose Expansion:

Metastatic Melanoma CPI Naïve

H0: iORR is 25%, at which the treatment is deemed as unacceptable.

H1: iORR is at least 40%, at which the treatment is deemed as acceptable.

Metastatic Melanoma CPI Refractory

H0: iORR is 13%, at which the treatment is deemed as unacceptable.

H1: iORR is at least 28%, at which the treatment is deemed as acceptable.

Ovarian

H0: iORR is 15%, at which the treatment is deemed as unacceptable.

H1: iORR is at least 30%, at which the treatment is deemed as acceptable.

Colorectal Cancer

H0: iORR is 18%, at which the treatment is deemed as unacceptable.

H1: iORR is at least 33%, at which the treatment is deemed as acceptable.

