2.2.1 Melanoma

Overall survival for advanced-stage melanoma of the skin has improved dramatically over the last decade from approximately 9 months before 2011 to at least 2 years in 2017 [[Luke et al, 2017](#)]. However, approximately 60% to 70% of patients that receive anti-programmed cell death protein 1 (anti-PD-1) therapy do not respond to treatment. Furthermore, acquired resistance is common, causing some patients who initially responded to the therapy to later experience disease progression. A recent study found that nearly 25% of patients with melanoma who initially had received an objective response had disease recurrence at follow-up (a median of 21 months) [[Simeone & Ascierto, 2017](#)]. Therefore, there is a high unmet need that persists for this patient population.

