3 OBJECTIVES, ENDPOINTS

Table 8 Study Objectives and Endpoints

Objectives	Endpoints
Primary	
• To evaluate the safety and tolerability of ASP7517 when administered as a single agent and in combination with pembrolizumab• To determine the RP2D and/or the MTD of ASP7517 when administered as a single agent and in combination with pembrolizumab (phase 1)• To evaluate the clinical response of ASP7517 when administered as a single agent and in combination with pembrolizumab (phase 2)
Secondary	
• Safety and tolerability as noted by: DLTs, AEs, SAEs, laboratory test results (serum, chemistry, hematology, coagulation and urinalysis, pregnancy test), ECGs, vital signs, physical exams and ECOG performance status scores• DLTs• Objective response rate per iRECIST (iORR) by independent central review• Objective response rate per RECIST v1.1 (ORR)• Disease control rate per iRECIST (iDCR) and RECIST v1.1 (DCR)• Progression-free survival per iRECIST (iPFS) and RECIST v1.1 (PFS)• Overall survival (OS)• Duration of response per iRECIST (iDOR) and RECIST v1.1 (DOR)
Exploratory	
• To evaluate potential genomic, proteomic and/or other biomarkers that may correlate with treatment outcome when ASP7517 administered as a single agent and in combination with pembrolizumab• Exploratory tumor and peripheral biomarkers that may correlate with treatment outcome of ASP7517 monotherapy or in combination with pembrolizumab

Table continued on next page

Objectives	Endpoints
Exploratory (continued)	

• To evaluate pharmacodynamic activities of ASP7517 as a single agent and in combination with pembrolizumab	
• Pharmacodynamic effects of ASP7517 as a monotherapy or in combination with pembrolizumab, such as changes in:
○ Cytokine expression and secretion (e.g., IFNγ)○ WT1-specific T lymphocytes (e.g., cytotoxic T lymphocytes)○ Immune cell populations (NKT cells, NK cells, etc.)○ Anti-WT1 antibodies○ Tumor microenvironment

• To characterize the pharmacokinetic profile of ASP7517 when administered as a monotherapy and in combination with pembrolizumab	
• Cellular DNA load and kinetic parameter estimates (including AUC, C_{max}, C_{trough} and t_{max}) for ASP7517 as a monotherapy or in combination with pembrolizumab

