4.1.6.2 Combination Therapy Arm Dose Expansion Cohort

The combination therapy arm dose expansion cohort will be opened after the phase 1 dose escalation cohort has been completed and MTD/RP2D of ASP7517 combination therapy has been determined. The metastatic melanoma CPI naïve cohort will be opened first. If 5 confirmed responses (iPR or iCR per independent central review) are observed in metastatic melanoma CPI naïve participants, expansion cohorts for CRC, ovarian cancer and metastatic melanoma CPI refractory may be opened. In addition, if a confirmed response (iPR or iCR per independent central review) is observed in metastatic melanoma CPI refractory participants in the monotherapy arm, an expansion cohort for melanoma refractory participants may be opened for combination arm therapy, if not yet opened.

For metastatic melanoma CPI naïve participants, initially 20 participants will be enrolled in an expansion cohort at each designated dose level (stage 1). If the iORR per independent central review does not meet the optimal stopping boundaries (see table below) for metastatic melanoma CPI naïve participants, then an additional 49 participants will be enrolled for a total maximum sample size of 69 at each dose level. When the total number of participants reaches the maximum sample size of 69, it may be predicted that the combination therapy with ASP7517 and pembrolizumab arm is effective if the number of responses is greater than or equal to 24.

Optimized Stopping Boundaries for Metastatic Melanoma (CPI Naïve) Combination Therapy Arm	
Number of participants treated	Stop if number of responses ≤
20	4

CPI: checkpoint inhibitor

For ovarian cancer, initially 19 participants will be enrolled in an expansion cohort at each designated dose level (stage 1). If the iORR per independent central review does not meet the optimal stopping boundaries (see table below) for ovarian cancer, then an additional 36 participants will be enrolled for a total maximum sample size of 55 at each dose level. When the total number of participants reaches the maximum sample size of 55, it may be predicted that the combination therapy with ASP7517 arm is effective if the number of responses is greater than or equal to 13.

Optimized Stopping Boundaries for Ovarian Cancer Combination Therapy Arm	
Number of participants treated	Stop if number of responses ≤
19	3

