4.2 Scientific Rationale for Study Design

This study was designed to evaluate ASP7517 as monotherapy and in combination with pembrolizumab in selected participants with advanced solid tumors known to express WT1 antigen. Antitumor efficacy of ASP7517 was demonstrated in preclinical AML model in which mice displayed significantly prolonged survival times.

The rationale for evaluating the combination of ASP7517 and pembrolizumab is supported by preclinical in vivo studies obtained from mice models that show superior antitumor activity of combination therapy over monotherapy. Longer survival period was shown by aAVC-WT1 treatment in combination with anti-PD1 antibody relative to aAVC-WT1 alone. The prolonged survival time most likely results from WT1-specific antitumor effect induced

by aAVC (NIH3T3)-WT1. This suggests additive activity of ASP7517 with CPIs like pembrolizumab, which are known to restore immune system tumor surveillance, while ASP7517 functions by stimulating the immune system. Therefore, combination therapy may lead to higher rates of response in cancer patients compared to monotherapy. However, the combination may also increase the frequency or severity of toxicities, and thus, a dose escalation study is the appropriate setting to explore this combination.

In this study, each participant will receive ASP7517 as monotherapy or in combination with pembrolizumab every 28 days.

The design will closely monitor safety while efficiently assessing efficacy of ASP7517 dose levels of 1×10^7 cells/dose and 1×10^8 cells/dose as monotherapy and in combination with pembrolizumab fixed dose of 400 mg every 6 weeks.

Tumor-specific expansion cohorts may be triggered by a confirmed response to ASP7517 or to the combination with pembrolizumab, or following the determination of RP2D. The types of cancer selected for the expansion cohorts were based on expression of WT1 in the tumor. Expansion will be initiated in melanoma (CPI naïve in the combination arm and CPI refractory in the monotherapy arm). A gated design in the expansion phase is being implemented to allow expansion into CRC and ovarian cancer. This gated design will allow early evaluation of response, avoiding a large number of participants being exposed to ineffective treatment. If antitumor activity is observed in dose escalation or melanoma dose expansion Stage 1, expansion cohorts for CRC and ovarian cancer may be opened.

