In the expansion phase of the combination arm, participants with metastatic melanoma are excluded if they received prior treatment with CPI. This will establish the efficacy of the combination of ASP7517 with pembrolizumab in CPI naïve participants. Also, there is no eligibility selection criteria for PD1 expression since it is not required per the pembrolizumab package insert for the tumor selected for the expansion phase.

In addition, participants with HIV will be excluded since the compromised immune system may affect the immune response of ASP7517.

Objective response rate (ORR) is selected as a suitable efficacy primary endpoint in such an early phase study because it can generally be assessed early and with a smaller sample size compared with survival studies. In addition, it provides an informative presentation of effect on tumor attributable to treatment since it is based on objective and quantitative assessment.

Based on the above, this study is designed appropriately to assess safety and efficacy of ASP7517 as monotherapy and in combination with pembrolizumab in the selected participants.

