5.1 Inclusion Criteria

Participant is eligible for participation in the study if all of the following apply:

1. Institutional Review Board (IRB)-/Independent Ethics Committee (IEC)-approved written informed consent and privacy language as per national regulations (e.g., HIPAA Authorization for U.S. sites) must be obtained from the participant prior to any study-related procedures (including withdrawal of prohibited medication, if applicable).
2. The participant is at least 18 years of age and legally an adult according to local regulation at the time of signing informed consent.
3. Participant has locally-advanced (unresectable) or metastatic solid tumor malignancy that is confirmed by available pathology records or current biopsy. Participant must also have received all standard therapies (unless the therapy is contraindicated or intolerable) appropriate to provide clinical benefit in the opinion of the treating investigator for his/her specific tumor type. However, participants with metastatic melanoma who have not received CPIs (i.e., CPIs naive) may enroll in the phase 2 Combination Therapy Arm Dose Expansion Cohort to receive CPI: Pembrolizumab.
4. Participant must be diagnosed with solid tumor known to express WT1 antigen such as, but not limited to melanoma, ovarian cancer or CRC (Examples of WT1 expressing cancers, please see literature reference by Sugiyama [2010]).
5. Participant consents to provide an archival tumor specimen in a tissue block or unstained serial slides, if available, prior to study treatment.
6. Participant has an Eastern Cooperative Oncology Group (ECOG) Performance Status of ≤ 2 .
7. Participant's last dose of prior antineoplastic therapy, including any immunotherapy, was 21 days or 5 half-lives, whichever is shorter, prior to initiation of IP administration. A participant with BRAF gene, epidermal growth factor receptor (EGFR) or anaplastic lymphoma kinase (ALK) mutation positive non-small cell lung carcinoma is allowed to remain on EGFR tyrosine kinase inhibitor (TKI) or ALK or BRAF inhibitor therapy until 4 days prior to the start of IP administration.
8. Participant has completed any radiotherapy (including stereotactic radiosurgery) at least 2 weeks prior to IP administration.
9. Participant's AEs (excluding alopecia) from prior therapy have improved to grade 1 or baseline within 14 days prior to start of IP.

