15. Male participant must not donate sperm during the treatment period and for 180 days after the final IP administration.
16. Male participant with pregnant partner(s) must agree to remain abstinent or use a condom for the duration of the pregnancy throughout the study period and for 180 days after the final IP administration.
17. Participant agrees not to participate in another interventional study while receiving IP.

Additional Inclusion Criteria for Participants in the Expansion Cohorts:

1. Participant meets one of the following:
 - Participant has the tumor type for which a confirmed response was observed in a monotherapy dose escalation cohort (monotherapy arm only) cohort; OR
 - For tumor specific expansion cohorts of ASP7517 or ASP7517 with pembrolizumab, participant has the applicable tumor type; CPI refractory metastatic melanoma (monotherapy and combination arms), CPI naïve melanoma (combination arm only), ovarian cancer, CRC.
2. Participant has at least 1 measurable lesion per response evaluation criteria in solid tumors (RECIST) v1.1. Lesions situated in a previously irradiated area are considered measurable if progression has been demonstrated in such lesions.
3. Participant consents to provide a tumor specimen in a tissue block or unstained serial slides obtained within 56 days prior to first dose of IP. If a recent tissue sample cannot be provided due to medical or safety concerns, enrollment into the study must be discussed with the medical monitor.
4. Participant consents to undergoing a tumor biopsy (core tissue biopsy or excision) during the treatment period as indicated in the schedule of assessments if predose biopsy is available and if medically feasible.

Waivers to the inclusion criteria will **NOT** be allowed.

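### Is the 25% null for the checkpoint-inhibitor-naive melanoma combination cohort too low, given the protocol's own account of response to anti-PD-1 therapy?

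*Protocol*

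**What the plan says.** Protocol Section 9.1 gives, for CPI-naive metastatic melanoma in the combination arm, "H0: iORR is 25%, at which the treatment is deemed as unacceptable", with an alternative of at least 40%. SAP Section 3 repeats both figures. Neither document says where 25% comes from. Protocol Section 9.2 states power of about 0.80 with a one-sided type I error of 0.05.

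Section 4.1.6.2 gives the rule. Twenty participants are enrolled, the cohort stops at 4 or fewer responses, and otherwise it continues to 69. Success needs 24 or more responses among the 69, and the conclusion is worded "it may be predicted that the combination therapy with ASP7517 and pembrolizumab arm is effective if the number of responses is greater than" that threshold allows.

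The background in Section 2.2.1 says that "approximately 60% to 70% of patients that receive anti-programmed cell death protein 1 (anti-PD-1) therapy do not respond to treatment". Under Section 5.1, CPI-naive patients "may enroll in the phase 2 Combination Therapy Arm Dose Expansion Cohort to receive CPI: Pembrolizumab". The expansion criteria list CPI-naive "melanoma (combination arm only), ovarian cancer, CRC", so this population has no arm without pembrolizumab.

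SAP version 2.0 (15-SEP-2023) records early closure. There is no independent central review (Section 5.1.1) and no interim analysis (Section 6.8). Investigator-assessed iORR is reported with a 95% Clopper-Pearson interval (Section 6.4.1.1).

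**The concern.** If 60% to 70% of patients do not respond to anti-PD-1 therapy, 30% to 40% do. A 25% null then lies below what pembrolizumab might achieve alone, and the 40% alternative lies at the top of that range. Everyone in the cohort receives pembrolizumab, so the rule could be met with ASP7517 contributing nothing.

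Two passages in Section 4.2 seem to raise the stakes. One says of the cohort "This will establish the efficacy of the combination of ASP7517 with pembrolizumab in CPI" naive participants. The other rests the combination rationale on mouse survival "in combination with anti-PD1 antibody relative to aAVC-WT1 alone". That comparison shows what anti-PD-1 adds to the vector cells, not the reverse. No passage warns the reader that 24 responses in 69 is compatible with pembrolizumab activity alone. The only other 25% in Section 2.2.1 is recurrence among initial responders, which cannot justify the null.

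At stake is whether a positive cohort would be taken as evidence for ASP7517.

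**Working it through.** **Inputs.** Null 0.25 and alternative 0.40 (Protocol 9.1, SAP 3). One-sided alpha 0.05 and power about 0.80 (Protocol 9.2). First stage of 20, stopping at 4 or fewer responses, then 49 more for a total of 69, with success at 24 or more (Protocol 4.1.6.2). Background response 30% to 40%, from 100% minus 70% and 100% minus 60% (Protocol 2.2.1).

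**Formula.** For a true response rate p, the probability of meeting the rule is

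S(p) = Σ (x = 5 to 20) C(20, x) p^x (1 − p)^(20 − x) × Pr[Bin(49, p) ≥ 24 − x].

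**The plan's own figures.** S(0.25) = 0.0418, below 0.05. S(0.40) = 0.8196, close to 0.80. Ignoring the futility look, the values are 0.0446 and 0.8432. The design does what Section 9.2 says.

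**The same rule at background rates, assuming no ASP7517 effect.**

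| True rate | Stops at 20 | Meets ≥24/69 |
|---|---|---|
| 25% | 0.415 | 0.042 |
| 30% | 0.238 | 0.216 |
| 33% | 0.159 | 0.400 |
| 35% | 0.118 | 0.536 |
| 40% | 0.051 | 0.820 |

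At 30% the rule still fails with probability 1 − 0.216 = 0.784. The 40% row is simply the design's power, since Section 9.1 deems that rate acceptable. The entries for 30% to 40% are type I errors only if pembrolizumab alone is made the reference, which the protocol does not do.

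**What a borderline success would look like in the report.** 24/69 = 34.8%, with a 95% Clopper-Pearson interval of 23.7% to 47.2%. The planned interval covers the whole 30% to 40% range, so the limit would be visible in the reported result.

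**What a higher null would buy.** Keep 69 participants and the same first-stage look, and take the smallest threshold with type I error at or below 0.05:

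| Null | Threshold | Type I error | Success at null + 15 points | Success at true 40% |
|---|---|---|---|---|
| 25% | 24 | 0.042 | 0.820 | 0.820 |
| 30% | 28 | 0.039 | 0.799 | 0.501 |
| 35% | 32 | 0.033 | 0.764 | 0.168 |
| 40% | 35 | 0.046 | 0.798 | 0.046 |

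A null of 30% costs 0.820 − 0.501 = 0.319 of the chance of success at a true 40%. The cohort would still be single-arm.

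**The case for a change.** The strongest case for a change is that it would be cheap. One sentence could justify the 25%, and another could say that meeting the rule does not isolate ASP7517. Section 2.2.1 goes on to discuss objective responses, so reading it as an objective response rate is natural, and Section 4.2 does expect more response from the combination than from monotherapy. There is also a knock-on effect. Under Section 4.1.6.2, five confirmed responses in this cohort may open the colorectal, ovarian and CPI-refractory combination cohorts. At a true 30%, at least 5 in the first 20 occurs with probability 1 − 0.238 = 0.762.

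It stands that the null is unexplained and that the cohort cannot separate the two drugs. The rest is weaker.

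- **The claim at issue is not made.** Section 4.1.6.2 says only that efficacy of the combination may be predicted. The statement in Section 4.2 about establishing efficacy explains why patients with prior CPI treatment are excluded, and it too concerns the combination. The phase 2 objective in Section 3 reads in full "To evaluate the clinical response of ASP7517 when administered as a single agent and in combination with pembrolizumab (phase 2"), which covers the combination and attributes nothing to one component.
- **The benchmark is loose.** Section 2.2.1 gives no line of therapy, no response criteria and no confirmation requirement. The cohort admits ECOG status up to 2 (Section 5.1) and stable treated CNS metastases (Section 5.2), and its endpoint is confirmed iRECIST response by central review (Section 9.4.2.1.1). The documents do not show whether the matching pembrolizumab-alone rate is above or below 30%.
- **The gate is permissive.** The later cohorts may be opened, not must be, and each has its own null and futility look.

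**Conclusion.** No change to the plan. The missing basis for 25% is a gap in explanation, and the level of the null is a fair trade-off for an early single-arm cohort. The design holds its stated error rates: 0.042 at 25% and 0.820 at 40%.

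The possible misreading has a definite but conditional size. The chance of meeting the rule without an ASP7517 effect is 0.22 if pembrolizumab alone gives 30% on this endpoint and 0.54 if it gives 35%. Those figures assume that the approximate background rate carries over to confirmed iRECIST response in these patients, which the documents cannot settle. No choice of null in a single arm would attribute response to ASP7517, and a higher null reduces the chance of advancing a combination with a true 40% rate.

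Events have also taken the practical weight off the point. SAP version 2.0 does not print the 24-of-69 rule and makes no success declaration, and the central review on which the stage decision rested is gone. Nothing in the documents shows that this cohort opened or reached 69. If it has data, an analyst would report the investigator-assessed iORR with its interval and say, as ordinary practice, that a single-arm combination rate does not isolate one drug. That sentence belongs in the study report and needs no revision of the protocol or SAP.

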9.2 Sample Size Determination

Phase 1 Dose Escalation:

The sample size of approximately 24, including 12 from monotherapy and 12 from combination therapy, is not based on a statistical power calculation. The number of participants enrolled will be dependent on the DLT incidence. The estimated number of participants should provide adequate information for the dose escalation and safety objectives of the study.

Phase 2 Dose Expansion:

It is estimated that up to approximately 361 participants may be enrolled in the monotherapy and combination therapy arms (approximately 129 participants for monotherapy and 232 participants for combination therapy). The iORR is monitored using the BOP2 design.

Monotherapy

For each indication, with assumptions mentioned in the [statistical hypotheses](#) section, the statistical power would be approximately 0.80 while controlling the type I error rate at 0.05 (1-sided).

Combination Therapy

For each indication, with assumptions mentioned in the [statistical hypotheses](#) section, the statistical power would be approximately 0.80 while controlling the type I error rate at 0.05 (1-sided).

9.3 Populations for Analyses

The following populations are defined:

Population	Description
Enrolled	All participants who sign the informed consent form are allocated to treatment
Full Analysis Set (FAS)	All participants who are enrolled and receive at least one dose of study treatment.
Response Analysis Set (RAS)	The RAS will consist of all participants who are enrolled and receive at least 1 dose of IP and have at least 1 post baseline primary efficacy measurement.
Safety Analysis Set (SAF)	All participants who take at least one dose of IP.
Pharmacokinetic analysis set (PKAS)	The PKAS consists of the administered population for which pharmacokinetics data are available for at least 1 time point. Additional participants may be excluded from the PKAS at the discretion of the pharmacokineticist.
Pharmacodynamic analysis set (PDAS)	The PDAS will include the participants from the administered population for whom sufficient pharmacodynamic measurements were collected. The PDAS will be used for all analyses of pharmacodynamic data.
DLT Evaluation Analysis Set (DEAS)	
The DEAS is defined as all participants in SAF by excluding participants who meet any of the following criteria:
 
• Participant is discovered to have enrolled without fully satisfying eligibility criteria.• Participant received less than the planned dose in Cycle 1 for reasons other than DLT.• Participant has no DLT and withdraws from the study before the end of DLT evaluation period 
The DEAS will be used for the analysis of DLT data.

DLT: dose limiting toxicity

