4.1.5.2 Phase 1 Dose Escalation Cohort for Monotherapy and Combination Therapy Arms

The monotherapy and combination therapy dose escalation portion will evaluate escalating dose levels of ASP7517 in approximately 9 to 12 DLT-evaluable participants.

Dose escalation will be guided according to the BOIN design [Liu & Yuan, 2015] to determine the next dose level based on DLT occurrence. After the planned number of evaluable participants has completed the DLT observation period for a given dose level, safety for that dose level will be assessed. Each dose level in the dose escalation will enroll

3 to 4 evaluable participants for the initial assessment of each dose level. Refer to the *Participant Replacement during Dose Escalation Cohort* section for definition of evaluable participants. If the decision is made to remain at the current dose level, an additional 3 or 4 evaluable participants may be enrolled at the current dose level. Three to 12 participants will be enrolled in the dose escalation cohort. A minimum of 6 participants must be enrolled at the dose level used to determine the maximum tolerated dose (MTD) and the recommended phase 2 dose (RP2D) of ASP7517.

Study enrollment and study treatment will be temporarily interrupted during dose escalation of monotherapy or combination therapy arms pending review of the following:

- Any death that is not related to disease progression occurring within 30 days of receiving IP
- Occurrence of 2 grade ≥ 4 DLTs in 2 study participants
- Any grade 4 hypersensitivity reaction/anaphylaxis

Participant Replacement during Dose Escalation Cohort

Participants may be replaced in the dose escalation cohort if:

- Participant is discovered to have enrolled without fully satisfying eligibility criteria
- Participant received less than the planned dose in Cycle 1 for reasons other than DLT
- Participant has no DLT and withdraws from the study before the end of DLT evaluation period

The decision regarding replacement of individual participants will be made by the sponsor with discussions with the treating investigator.

Participants who experience DLTs in the dose escalation cohort will not be replaced.

Refer to [\[Section 10.1.5.1 Dose Escalation and Safety Committee\]](#) for details about the DESC.

Maximum Tolerated Dose

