The MTD determination will be based on at least 6 evaluable participants at that dose level based on the BOPIN design. Based on the observed DLT(s) during the DLT observation period, the MTD is the highest dose for which the isotonic estimate of the DLT rate is closest to, but not over, the target DLT rate of 0.30 for monotherapy and combination therapy.

The dose level determined to be the MTD must have data from at least 6 participants. Determination of MTD will be done for monotherapy and combination therapy separately.

Recommended Phase 2 Dose

The sponsor, in conjunction with the DESC, will determine the RP2D of ASP7517 as a single agent and in combination with pembrolizumab taking into consideration the safety and efficacy data, as well as other available data, such as pharmacokinetics and pharmacodynamics of ASP7517. The RP2D will not exceed the MTD.

The dose level determined to be the RP2D must have data from at least 6 participants. Determination of RP2D will be done for monotherapy and combination therapy separately.

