6.5.1 Dose Limiting Toxicities

Dose evaluation and dose escalation stopping rules based on the BOPIN design with target DLT rate of 0.30 and optimal interval of (0.236, 0.359) are as follows:

Action	Number of Participants Treated at Current Dose Level					
	3	4	5	6	7	8
Escalate dose if number of participants with DLT \leq	0	0	1	1	1	1
Stay at current dose level if number of participants with DLT =	1	1	-	2	2	2
De-escalate if number of participants with DLT =	2	2	2 or 3	3	3 or 4	3 or 4
Stop if number of participants with DLT \geq	3	3	4	4	5	5

DLT: dose limiting toxicity

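### Two of the three DEAS exclusions can drop a participant with a confirmed DLT, and the plan does not settle which set the DLT summary and the MTD estimate use

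*Protocol*

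**What the plan says.** **The set.** Protocol 9.3 takes the Safety Analysis Set (SAF) and removes anyone who meets any one of three criteria:

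1. "Participant is discovered to have enrolled without fully satisfying eligibility criteria". DLTs are not mentioned.
2. Less than the planned Cycle 1 dose, unless a DLT was the reason.
3. Withdrawal before the DLT window ends, but only where no DLT occurred.

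The same table row adds: "The DEAS will be used for the analysis of DLT data". SAP 4 repeats the definition.

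**Replacement.** The synopsis and protocol 4.1.5.2 give the same three criteria as grounds on which a participant may be replaced, then state: "Participants who experience DLTs in the dose escalation cohort will not be replaced".

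**Counts for escalation and MTD.** Protocol 4.1.5.2 refers the reader to the replacement "section for definition of evaluable participants". The action table in the synopsis and SAP 6.5.1 is headed "Number of Participants Treated at Current Dose Level". For the MTD the protocol says "The MTD determination will be based on at least 6 evaluable participants at that dose level based on the BOPIN design" and also "The dose level determined to be the MTD must have data from at least 6 participants". No set is named for the isotonic estimate.

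**Reporting.** SAP 6.5 runs safety analyses on the SAF, and SAP 6.5.2, within that section, lists a summary of DLTs in the observation window. SAP 4 assigns DLT data to the DEAS.

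**The concern.** The third exclusion keeps every participant who had a DLT. The first keeps none, and the second keeps only those whose under-dosing came from the DLT. Two kinds of participant with a confirmed DLT therefore fall out of the DEAS: one found ineligible afterwards, and one under-dosed for an unrelated reason who then had a DLT. Neither is replaced, so the DEAS at that dose shrinks by one participant and one event.

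DLTs are a primary endpoint and the cohorts are small, so one omitted event moves the reported rate a good deal. The DEAS rate could also differ from the counts used when the dose decision was made, with no rule for saying which is the result.

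The plan foresees late-found ineligibility. Protocol 8.1 allows some such participants to stay only if they have clinical benefit and no DLT, and SAP 6.2.2 has a deviation category for entry-criteria failures.

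**Working it through.** **1. The plan's own figures.** With target 0.30 and assumed BOIN settings of 0.6 × 0.30 = 0.18 and 1.4 × 0.30 = 0.42, the boundaries are

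- lower: log(0.82/0.70) / log[(0.30 × 0.82)/(0.18 × 0.70)] = 0.2365
- upper: log(0.70/0.58) / log[(0.42 × 0.70)/(0.30 × 0.58)] = 0.3585

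These match the stated interval (0.236, 0.359). Adding an assumed stopping rule, a posterior probability above 0.95 that the rate exceeds 0.30 under a Beta(1,1) prior, reproduces every cell of the action table for 3 to 8 participants. The table is not in question; which participants enter it is.

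**2. Who is dropped (participants with a confirmed DLT).**

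| Other circumstance | In DEAS? | Replaced? |
|---|---|---|
| Withdrew early | Yes | No |
| Under-dosed because of the DLT | Yes | No |
| Under-dosed for another reason | No | No |
| Found ineligible later | No | No |

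**3. Effect on the DEAS rate.** Protocol 4.1.5.2 plans 3 or 4 evaluable participants per dose and, on a stay decision, says "an additional 3 or 4 evaluable participants may be enrolled at the current dose level". The planned sizes are thus 3, 4, 6, 7 or 8. Dropping one participant with a DLT turns x/n into (x − 1)/(n − 1), a fall of (n − x)/[n(n − 1)].

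| Kept | Dropped | Fall |
|---|---|---|
| 1/4 = 0.250 | 0/3 = 0.000 | 0.250 |
| 2/6 = 0.333 | 1/5 = 0.200 | 0.133 |
| 3/7 = 0.429 | 2/6 = 0.333 | 0.095 |
| 3/8 = 0.375 | 2/7 = 0.286 | 0.089 |

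The rate never rises.

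**4. How often.** The documents give no rate of late-found ineligibility. Assume 1% to 5% per participant, a DLT rate d of 0.05 to 0.30, and independence. For 12 participants in an arm, the chance of at least one ineligible participant with a DLT is 1 − (1 − d × e)^12, where e is the ineligibility rate:

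- d = 0.05, e = 0.01: 0.6%
- d = 0.30, e = 0.05: 16.6%

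The upper end needs both assumptions at their limit. Under-dosing for other reasons is not included, because the documents give no basis for a figure.

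**5. Price of the fix.** Suppose one of n participants is ineligible, independently of toxicity, and the true DLT rate is p. Under the present rule that participant is always dropped and the expected rate is p. Under the fix the participant stays if there was a DLT (rate (1 + X)/n, with X binomial on n − 1) and is dropped otherwise. The expected rate is

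p × [1 + (n − 1)p]/n + (1 − p) × p.

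At p = 0.30:

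| n | 3 | 4 | 6 | 7 | 8 |
|---|---|---|---|---|---|
| Expected rate | 0.370 | 0.353 | 0.335 | 0.330 | 0.326 |

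For n = 8: 0.30 × 3.1/8 + 0.21 = 0.116 + 0.210 = 0.326.

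**The case against.** **The asymmetry may be deliberate.** A DLT can cause under-dosing or withdrawal; it cannot cause ineligibility at entry. Dropping ineligible participants whatever their outcome leaves the expected rate at 0.300, while keeping them only if they had a DLT selects on outcome. This stands as a real trade-off. But the third exclusion already keeps participants by DLT status, so the fix follows the plan's own convention, and the shift is in the cautious direction.

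**Both rules can be followed.** One governs enrolment, the other analysis. That is correct. The effect is a DEAS one participant and one event smaller, not an impossible instruction.

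**The event is still reported.** It stays in the SAF, SAP 6.5.2 lists adverse events and a DLT summary, and the Dose Escalation and Safety Committee considers all available safety findings. This stands, so it is not established that the DLT summary omits the event. What remains is that SAP 4 and SAP 6.5 point to different sets.

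**A stronger reading.** A reader might infer that the omission changes dose decisions or the MTD: 3/8 reads as de-escalate and 2/7 as stay, and only the second rate is below 0.30. The documents do not support that. Nothing ties the DEAS to the BOIN counts or the isotonic estimate. The action table counts treated participants, and the section that defines evaluable keeps participants with a DLT in place. Even if the counts did follow the DEAS, a change such as 1/4 (stay) to 0/3 (escalate) would mean nothing at the top planned dose, which has no higher level. Nor need a fall from 6 to 5 block the MTD minimum, since a stay decision allows more enrolment.

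**It is late.** SAP 5.1.1 and 7 record early closure, and a SAP edit cannot change past escalation decisions. This stands and limits the benefit to final reporting.

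**Conclusion.** The point holds as a minor gap in the definition of an analysis set. Read as written, protocol 9.3 and SAP 4 remove a confirmed DLT from the DEAS in two situations, and the participant is not replaced. One such case lowers the DEAS rate at that dose by 0.089 (3/8 to 2/7) to 0.250 (1/4 to 0/3) in the examples above.

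The case should be rare. Protocol 5 requires eligibility to be confirmed at screening and allows no waivers, and protocol 4.3.1 reports no DLTs in the earlier single-agent study. The 0.6% to 16.6% range rests on assumed rates and covers ineligibility only.

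Whether BOIN counts or the MTD are touched is not stated, and no effect on them is claimed here. What is at stake is that the final DLT rate includes every confirmed DLT and comes from one named set.

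**What to change.** - In SAP 4, and in protocol 9.3 if it is amended, apply exclusions 1 and 2 only to participants with no DLT. This reconciles the DEAS with the no-replacement rule.
- Name one set for the DLT summary in SAP 6.5.2 and for the isotonic MTD estimate in SAP 5.2.1.4.
- Justify the departure from protocol 9.3 in the clinical study report, as protocol 9.4 and SAP 1 provide.

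The cost is two short wording changes and one sentence before database hardlock, plus the report note. If no such participant exists, the exclusion wording changes no result. If one ineligible participant does, the DLT rate shifts upward as in step 5. That calculation does not cover an under-dosed participant, whose DLT risk may differ from that at the planned dose.
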